Implant, abutment, and restoration in situ at time of the study visit and no ADEs related to the reconstruction or adjacent peri-implant tissues reported from the day when the study position(s) was permanently included in a prosthetic restoration until the end of the study.

- Bone tissue response

Marginal Bone Levels (MBL) from radiographs.

- Soft tissue response

Probing Pocket depth (PPD) Bleeding on Probing (BoP) Presence of Plaque.

- Patient reported outcomes

Subjects rate 1) Chewing function, 2) Esthetics and 3) Satisfaction.

- Adverse Device Effects (ADE) and Serious Adverse Device Effects (SADE)

Adverse Device Effects related to implant, abutment, restoration, or adjacent peri-implant tissues reported from the day when the study implant(s) was installed until the end of the study.

Study design

This study is designed as a retrospective and multi-center study. The study population consist of subjects who received one or more OsseoSpeed EV implants during the period January 1st 2015 to December 31st 2016. Two hundred subjects will be enrolled, approximately 25-30 subjects per site. The study includes retrospective data collection from subjects' medical records and data collection from one prospective study visit with clinical examination.

The active study phase, at each study site, is estimated to 6 months and includes: contacting the subjects identified and randomized during the screening phase, recalling the subjects to the clinic to perform one study visit. During this visit the informed consent form (ICF) will be signed and the clinical examination will be performed.

The study starting date for each enrolled subject will be the date the ICF is signed, and the study ends when he/she finalize the prospective study visit.

Study population

The study population will include subjects that received OsseoSpeed EV implants during January 1st 2015 to December 31st 2016. At least 6 study sites will be needed to enroll the required number of subjects.

The study subjects will be recruited from the clinics' full population of individuals previously treated with OsseoSpeed EV implants, replacing one or more teeth, anywhere in the mouth as part of their prosthetic restorations. The implants evaluated in this study will all have been placed according to the standard practice for treatment with OsseoSpeed EV implants.

Inclusion criteria

For inclusion in the study subject must meet all of the following criteria:

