1. Subject \geq 18 years at time of implant installation.
2. Subject signed and dated the informed consent form.
3. Having installed one or more OsseoSpeed EV implants between January 1st 2015 and December 31st 2016.

Exclusion criteria

Any of the following is regarded as a criterion for exclusion from the study:

1. Unlikely to be able to comply with study procedures, according to Investigators judgment.
2. Subject is not willing to participate in the study or not able to understand the content of the study.
3. Involvement in the planning and conduct of the study.
4. Simultaneous participation in another clinical study that may interfere with the present study.
5. Severe non-compliance to CIP as judged by the Investigator and/or Dentsply Sirona Implants.

Study products

The investigational product (OsseoSpeed EV implant) is already included in a restoration in the subject at enrollment, thus this study does not involve the installation of any investigational products.

Indication

Implant used for single, partial or full-prostheses.

Statistical methods

General

If nothing else is stated, descriptive statistics will be given for each variable in the study. This means number of subjects or study positions (n), mean, median, standard deviation (SD), minimum (min) and

maximum (max) values will be presented for continuous data and frequencies and percentages for categorical data.

In relation to objectives

The primary analysis of the study is to estimate the proportion of implants not failing (i.e., survive) over a fixed period of time. Each study position will be categorized as survived (Yes/No). Position will be categorized as survived = Yes, when the implant has been in situ during study. Position will be categorized as survived = No, when the implant has been lost during study. The proportion of survived study positions will be calculated by dividing the number of study positions with survived=Yes, by the total number of study positions. This proportion will be presented together with a 95% confidence interval (using the exact Binomial approach) independent of the follow-up time.

The primary analysis of the study is to estimate the proportion of implants/subjects not failing (i.e., survive).

The expected (i.e., the true) survival rate of the implants is denoted Π and is assumed to be 97 %. The null-hypothesis that the survival rate is less than 91% will be tested using the exact Binomial test, i.e. the following hypotheses will be tested:

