$$H_0: \Pi < 91 \%$$

versus

$$H_1: \Pi \geq 91 \%$$

Survival will be calculated on a study position level although the sample size calculation provides the number of subjects needed; this approach is chosen since we do not in advance know the number of study positions per subject. Consequently, we assume that study positions within one subject are independent of each other if more than one.

Implant survival will be analyzed on an implant level (i.e., percent of survived implants) as well as on subject level (i.e., percentage of subjects with no lost implants) i.e., if one or more implant(s) fail within a subject the subject is considered as a failure.

Primary analysis will be done on implant level.

Study timetable

Anticipated First Site Initiated:	2019 January
Anticipated Last Site Initiated:	2019 February
Anticipated First Subject Enrolled:	2019 February
Anticipated Last Subject Last visit:	2019 August
Anticipated Data Base Lock:	2019 September

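### The primary exact binomial interval and test treat all implants as independent, although subjects are sampled and may each have several implants

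*Combined protocol and SAP*

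**What the plan says.** All references are to the combined protocol and SAP.

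- **Sampling unit** (Study design): "Two hundred subjects will be enrolled, approximately 25-30 subjects per site".
- **Implants per subject** (Study population): subjects are recruited from patients treated with implants "replacing one or more teeth, anywhere in the mouth as part of their prosthetic restorations". The Indication section covers single, partial and full prostheses. No mean or distribution of implants per subject is given.
- **Primary analysis** (Statistical methods, In relation to objectives): surviving study positions are divided by all study positions. On the interval: "This proportion will be presented together with a 95% confidence interval (using the exact Binomial approach) independent of the follow-up time". On the test: "The null-hypothesis that the survival rate is less than 91% will be tested using the exact Binomial test". The implant-level result is named as primary.
- **Independence** (same section): survival is calculated by position, whereas for planning "the sample size calculation provides the number of subjects needed". The reason offered for working by position is: "this approach is chosen since we do not in advance know the number of study positions per subject". The next sentence reads: "Consequently, we assume that study positions within one subject are independent of each other if more than one".
- **Subject-level analysis** (same section): also planned, counting a subject as a failure if any implant is lost.

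No cluster-adjusted variance, model or resampling method appears anywhere.

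**The concern.** Implants in one subject share the host, usually the clinician, and often the restoration, so positive correlation of losses is a reasonable expectation. The plan sets this correlation to zero, and the only ground in the text is that implant counts are unknown at the design stage. That limits the sample size calculation. It does not bear on whether losses are correlated, and the counts will be known at database lock, when the analysis can use them.

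Under positive correlation the pooled proportion is still a sound estimate, but its binomial variance is too small. Two results are at stake: the coverage of the reported 95% interval, and the type I error of the test when true survival is near 91%.

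**Working it through.** **1. What the plan's own figures imply.** The documents give 200 subjects, 97% expected survival and a 91% threshold, but no alpha, sidedness or power, so 200 cannot be formally reproduced. With 200 independent units and an assumed one-sided 2.5% exact test, rejection needs at least 191 of 200 in situ; type I error is 1.2% and power at 97% is 91.9%. At one-sided 5% the figures are 189, 4.7% and 98.2%.

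**2. Same total, different loss patterns.** This needs no assumed correlation, only an assumed mix: 100 subjects with one implant, 50 with two, 30 with three, 10 with four and 10 with six. Then S = 200 subjects, N = 100 + 100 + 90 + 40 + 60 = 390 implants, and Σm² = 100 + 200 + 270 + 160 + 360 = 1,090. Suppose 12 are lost: p = 378/390 = 0.9692 and q = 1 − p = 0.0308.

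- Naive variance: p(1 − p)/N = 7.65 × 10⁻⁵.
- Between-subject variance: S/(S − 1) × SS/N², where SS = Σ(lossᵢ − mᵢq)² = Σloss² − 2qΣ(loss × m) + q²Σm², and q²Σm² = 1.03.
- deff = between-subject variance / naive variance; effective sample size = N/deff, capped at N; then a Clopper-Pearson interval.

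| Pattern of the 12 losses | SS | deff | N/deff | Clustered 95% CI |
|---|---|---|---|---|
| 12 single-implant subjects lose one each | 12 − 0.74 + 1.03 = 12.29 | 1.06 | 367 | 94.6–98.4% |
| three two-implant subjects lose both; six single-implant subjects lose one | 18 − 1.11 + 1.03 = 17.92 | 1.55 | 252 | 94.0–98.7% |
| one six-implant subject loses all six; six single-implant subjects lose one | 42 − 2.58 + 1.03 = 40.45 | 3.50 | 112 | 91.8–99.3% |

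The planned interval is 94.7–98.4% in all three rows: it cannot tell these datasets apart.

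**3. Operating characteristics.** Beta-binomial losses within subject with intraclass correlation ρ, 200 subjects, 100,000 replicates per scenario, implant counts redrawn each time. H0 is rejected if the lower 95% limit exceeds 91%. The mixes are assumptions:

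- base: 50/25/15/5/5% with 1/2/3/4/6 implants, mean 1.95;
- mostly single: 80/15/5% with 1/2/3, mean 1.25;
- more full-arch: 45/25/10/10/10% with 1/2/3/4/6, mean 2.25.

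The theoretical design effect is 1 + (E[m²]/E[m] − 1)ρ, with E[m²]/E[m] = 2.79, 1.48 and 3.36. For the base mix at ρ = 0.5 it is 1 + 1.79 × 0.5 = 1.90. Adjusted means the interval of step 2.

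| Mix | ρ | Coverage at 97%: planned / adjusted | Type I error at 91%: planned / adjusted | Adjusted power at 97% |
|---|---|---|---|---|
| Base | 0 | 96.5 / 96.7% | 2.1 / 1.9% | 99.9% |
| Base | 0.2 | 93.0 / 95.8% | 3.8 / 2.5% | 98.0% |
| Base | 0.5 | 87.7 / 94.9% | 6.7 / 2.9% | 90.7% |
| Mostly single | 0 | 96.4 / 96.5% | 1.8 / 1.7% | 97.8% |
| Mostly single | 0.2 | 95.6 / 96.3% | 2.3 / 2.0% | 96.0% |
| Mostly single | 0.5 | 94.0 / 95.7% | 3.0 / 2.2% | 92.3% |
| More full-arch | 0 | 96.4 / 96.6% | 2.1 / 1.9% | 100.0% |
| More full-arch | 0.2 | 91.7 / 95.6% | 4.5 / 2.7% | 98.4% |
| More full-arch | 0.5 | 84.8 / 94.1% | 8.2 / 3.1% | 91.0% |

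**4. Cross-check without simulation.** Exact convolution with three implants in every subject and ρ = 0.3 gives type I error 5.9% and coverage 88.6% at 91% survival, against 2.4% and 95.4% under independence. With two implants each and ρ = 0.1, type I error is 2.3%, still under 2.5% because the exact test is conservative.

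**The case against.** **The plan is open about the assumption and adds a subject-level analysis.** True, and that analysis is free of within-subject clustering. If tested against 91%, it would reject in at most 0.4% of trials when implant survival is 91%. But it estimates another quantity: under independence, 97% per implant means 0.97² = 94.1% of subjects with two implants and 0.97³ = 91.3% with three. Its power at 97% implant survival is only 29–70% in the base mix. It is conservative support and does not correct the primary interval or test.

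**The unknown counts explain the choice of position level, not independence.** This reading is possible, although the wording ties the two together. On this reading the plan gives no justification for independence at all, which does not help it.

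**The size is unknown, and the expected decision is safe.** This stands. Material harm needs many multi-implant subjects and a correlation of about 0.2 or more. At 97% survival the planned and adjusted decisions differ in 1.4–1.7% of trials at ρ = 0.2 and 4.3–8.1% at ρ = 0.5. Rejection is correct there, so these differences are power lost to the adjustment and not errors of the planned test. The case rests on coverage and on type I error near 91%.

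**The remedy is imperfect.** Also true. With implant counts held fixed instead of redrawn, the worst adjusted coverage (more full-arch, ρ = 0.5) is about 93.5–93.8% instead of 94.1%; the planned interval has about 85%. With no losses there is nothing to adjust.

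**Conclusion.** The concern holds and should be fixed. The independence assumption is explicit, unsupported, and governs both the primary interval and the primary test. The direction of the error follows from positive correlation. Its size rests on assumed mixes, assumed ρ of 0 to 0.5 and an assumed one-sided 2.5% level: coverage from about 96% down to 84.8%, and type I error from about 2% up to 8.2%. It is minor if most subjects have one implant. The point estimate is unaffected, and the conclusion at 97% survival would seldom change.

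**What to change.** - Delete the independence sentence and keep the implant-level proportion as the primary estimate.
- Pre-specify one subject-clustered 95% interval and its matching test as primary, rejecting H0 if the lower limit exceeds 91%. The effective-sample Clopper-Pearson interval above is one choice. A GEE interval (logit link, independence working correlation, variance robust by subject) is an acceptable alternative with the same point estimate. A Wald interval on the proportion scale is not suitable.
- State the rule for no losses, when deff cannot be estimated: report the exact lower limit on N, with the exact limit on the number of subjects as a conservative bound. For 390 implants in 200 subjects these are 0.025^(1/390) = 99.1% and 0.025^(1/200) = 98.2%.
- Report the naive exact result, the implants-per-subject distribution and the estimated deff as supportive. Keep the subject-level analysis as secondary.

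**Cost.** SAP wording and a few lines of code; no extra data or subjects. In the base, mostly single and more full-arch mixes the interval widens by 16, 5 and 21% at ρ = 0.2, and by 38, 11 and 48% at ρ = 0.5. Adjusted power at 97% stays at or above 90.7%, close to the 91.9% for 200 independent units.

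**Limits.** With about 390 × 0.03 ≈ 12 losses expected, deff is imprecise (base mix, ρ = 0.2: 95% of estimates between 0.96 and 2.19). If losses concentrate in one subject, the lower limit can rise with further losses elsewhere: 91.7% with six in one subject, 92.1% after three more single losses (GEE: 89.9% and 91.5%). This is why deff and the naive result belong beside the primary result.
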